10.3.2.10 Hospital Anxiety and Depression Scale

The HADS is a Likert-scale tool widely used to detect states of anxiety and depression in a general hospital setting (33). The tool consists of 14 items that assess the subject's anxiety (7 items) and depression (7 items) during the last week. Each question is scored from 0 to 3, with high scores indicating a poor state. The HADS will be completed electronically on the device supplied to the trial site according to the schedule of procedures (Section 4). The HADS is included in the investigator trial file.

10.4 Safety assessments

10.4.1 Vital signs

Vital signs (resting blood pressure, pulse, and body temperature) must be assessed according to the schedule of procedures (Section 4). Vital signs will be measured in supine position following at least 5 minutes' rest.

For the first 3 IMP dosing visits in both the initial treatment period (i.e., Weeks 0, 2, and 4) and the continuation treatment period (i.e. Weeks 16, 18, and 20), subjects will be monitored after IMP administration for immediate drug reactions for a minimum of 30 minutes with vital signs taken at 30 minutes or until stable, whichever is later (Section 9.1.3.1).

If an abnormal vital sign at screening is considered by the investigator to be clinically significant, it will be at the investigator's discretion if the subject should be randomised into the trial (respecting exclusion criterion no. 26).

In case of abnormal findings, the vital sign measurement can be repeated approximately 15 minutes later with subjects resting in a supine position to verify the first measurement. Should the repeated measurement result in a normal value, the measurement must be repeated once more. If the third measurement verifies the second (normal) value, the first measurement should be considered as false. If the third measurement confirms the first measurement (abnormal) the second measurement will be considered as false. Only the last value measured and considered as correct will be recorded in the eCRF.

Trial ID: LP0162-1339	Date: 29-Aug-2018	Version: 4.0
		Page 72 of 129

Clinically significant abnormal vital signs at the first screening visit will be documented as medical history in the eCRF. If an abnormal vital sign at any other visit than the first screening visit is considered by the investigator to be clinically significant, it will be reported as an AE in accordance with Section 11.2. Further, any clinically significant deterioration of a pre-existing condition as well as any new clinically significant sign, symptom or illness observed after screening will be reported as an AE in accordance with Section 11.2.

10.4.2 Physical examination

A thorough physical examination of the subject including whole body inspection of the skin and auscultation of heart, lungs and abdomen; palpation of the abdominal organs and basic neurological status must be performed according to the schedule of procedures (Section 4).

If an unacceptable abnormal finding is identified during the physical examination at the screening visit, the subject must not be randomised into the clinical trial (respecting exclusion criterion no. 26).

Clinically significant abnormal physical examination findings at the first screening visit will be documented as medical history in the eCRF. If an abnormal finding at any other visit than the first screening visit is considered by the investigator to be clinically significant, it will be reported as an AE in accordance with Section 11.2. Further, any clinically significant deterioration of a pre-existing condition as well as any new clinically significant sign, symptom, or illness observed after screening will be reported as an AE in accordance with Section 11.2.

10.4.3 Digital ECG

A single 12-lead resting digital ECG will be recorded after the subject has been supine for at least 5 minutes at the visits indicated in the schedule of procedures (Section 4).

A pre-evaluation of the ECGs will be performed by the investigators to evaluate immediate subject safety. At a minimum, date of ECG collection will be recorded in the source documents.

The ECG data will be transferred to a central ECG service company for central evaluation. A cardiologist at the ECG service company will analyse and interpret the ECG data. The ECG service company will provide ECG evaluation reports to the trial sites.

The investigator must evaluate all abnormal ECG results ('clinically significant' or 'not clinically significant') and sign and date. The investigator has the final decision on the clinical

Trial ID: LP0162-1339	Date: 29-Aug-2018	Version: 4.0
		Page 73 of 129

significance of ECG abnormalities. If a result is abnormal at the screening visit and considered by the investigator to be clinically significant, it will be up to the investigator's discretion if the subject should be enrolled into the trial (respecting exclusion criterion no. 26); if such a subject is enrolled, the investigator will provide a justification in the medical record.

Clinically significant abnormal ECG findings at the first screening visit will be documented as medical history in the eCRF. If an abnormal ECG finding at any other visit than the first screening visit is considered by the investigator to be clinically significant, it will be reported as an AE in accordance with Section 11.2. Further, any clinically significant deterioration of a pre-existing condition as well as any new clinically significant sign, symptom, or illness observed after screening will be reported as an AE in accordance with Section 11.2.

Test dummy transmissions will be undertaken prior to trial conduct to ensure that transmissions can be made and that date and time settings are correctly set.

The collection and transmission of ECG data will be described in a separate ECG manual.

10.4.4 Pregnancy test

A serum pregnancy test must be taken at the screening visit in female subjects of child-bearing potential as described in the schedule of procedures in Section 4.

A urine pregnancy test (human chorionic gonadotropin; dipstick) must be performed at the trial site at baseline prior to randomisation in female subjects of child-bearing potential. The test must be repeated every 4 weeks as shown in the schedule of procedures in Section 4.

Note that pregnant subjects must discontinue the IMP and NIMP immediately (Section 9.7.1).

10.4.5 Laboratory testing

The following safety samples will be analysed by a central laboratory: chemistry, haematology, serology, and serum pregnancy, see Panel 9 for an overview of the individual laboratory parameters assessed in this trial. Urine samples will be tested at the trial site with a dipstick; if abnormal, a urine sample will be sent to the central laboratory for further analysis.

A laboratory manual will be provided to the sites that specifies the procedures for collection, processing, storage, and shipment of samples, as well as laboratory contact information specific to this trial.

Trial ID: LP0162-1339	Date: 29-Aug-2018	Version: 4.0
		Page 74 of 129

Samples for laboratory testing will be collected according to the schedule of procedures (Section 4).

The investigator must evaluate all results outside the reference range ('clinically significant' or 'not clinically significant') and sign and date. The signed and dated version will be filed with the investigator's trial documentation. Clinically significant abnormal tests must be repeated to confirm the abnormality.

Panel 9 Central laboratory testing

Chemistry	Haematology	
Sodium	Erythrocytes	
Potassium	Haematocrit	
Creatinine	Haemoglobin	
Urea nitrogen	Erythrocyte mean corpuscular volume	
Calcium	Erythrocyte mean corpuscular haemoglobin concentration	
Alkaline phosphatase	Leukocytes	
Aspartate aminotransferase	Neutrophils, neutrophils/total cells	
Alanine aminotransferase	Lymphocytes, lymphocytes/total cells	
Gamma glutamyl transferase	Monocytes, monocytes/total cells	
Bilirubin ¹	Eosinophils, eosinophils/total cells	
Lactate dehydrogenase	Basophils, basophils/total cells	
Cholesterol	Thrombocytes	
LDL cholesterol	Serology	
HDL cholesterol	Hepatitis B virus surface antigen ⁴	
Triglycerides	Hepatitis B virus surface antibody ⁴	
Glucose (non-fasting)	Hepatitis B virus core antibody ⁴	
Albumin	Hepatitis C virus antibody ⁴	
Protein	HIV-1 antibody ⁴	
Tryptase ²	HIV-2 antibody ⁴	
	Immunoglobulin E ⁵	
Urinalysis ³	Serum pregnancy test (females only) ⁴	
Protein	Choriogonadotropin beta	
Glucose		
Ketones		
Occult blood		
Leukocytes		
Nitrite		

- 1) If bilirubin is above upper limit of normal, direct and indirect bilirubin will also be measured.
- 2) Only measured in case of suspected anaphylaxis (Section 9.1.3.1).
- 3) Urine samples will be tested at the trial site (dipstick). In case of abnormal dipstick results, a urine sample will be sent to the central laboratory for microscopic examination (leukocytes, erythrocytes, and casts).
- 4) Measured at screening only.
- 5) Not measured at screening.

Abbreviations: HDL, high density lipoprotein; LDL, low density lipoprotein.

Trial ID: LP0162-1339	Date: 29-Aug-2018	Version: 4.0
		Page 75 of 129

The central laboratory will provide results in SI units to trial sites in Europe and in conventional units to sites in North America; results that are transferred to the trial database will be in SI and conventional units.

Handling, storage, destruction and shipment instructions are provided in a separate laboratory manual.

If a screening laboratory result is abnormal and of clinical significance, it will be at the investigator's discretion to decide if the subject should be enrolled into the trial (respecting exclusion criteria no. 26, 27, and 28).

Clinically significant abnormal laboratory findings at the first screening visit will be documented as medical history in the eCRF. If an abnormal finding at any other visit than the first screening visit is considered by the investigator to be clinically significant, it will be reported as an AE in accordance with Section 11.2. Further, any clinically significant deterioration of a pre-existing condition as well as any new clinically significant sign, symptom or illness observed after screening will be reported as an AE in accordance with Section 11.2.

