Panel 2 Schedule of trial procedures: screening and treatment periods (continued)

									Tre	atm	ent p	erio	d							
	Scree	ning			In	itial	trea	tmer	ıt				Coı	ntinu	atio	n tre	atm	ent		Details
Visit	1 ¹	2	3	4	5	6	7	8	9	10	11	12	13	14	15	16	17	18	19	(protocol section)
Week	-6	-2	0	2	4	6	8	10	12	14	16	18	20	22	24	26	28	30	32	
Visit window (days) ²	±3	-3	NA	±3	±3	±3	±3	±3	±3	±3	±3	±3	±3	±3	±3	±3	±3	±3	±3	
Subject assessment of efficacy																				
eDiary training		X																		10.3.2
eDiary completion ⁷			<-=															->		
POEM			X	X	X	X	X		X		X		X				X		X	10.3.2.7
DLQI			X	X	X	X	X		X		X		X				X		X	10.3.2.8
EQ-5D-5L, HADS			X		X		X		X		X		X				X		X	10.3.2.9, 10.3.2.10
Safety assessments																				
Vital signs	X		X ⁶	X ⁶	X ⁶	X	X	X	X	X	X ⁶	X^6	X ⁶	X	X	X	X	X	X	10.4.1
Physical examination	X		X				X				X								X	10.4.2
ECGs	X		X				X				X				X				X	10.4.3
Serum pregnancy test, hepatitis B, C, HIV	X																			10.4.4, 10.4.5
Urine pregnancy test			X		X		X		X		X		X		X		X		X	10.4.4
Serum chemistry, haematology, IgE	X8		X		X		X		X		X		X		X		X		X	10.4.5
Urinalysis	X		X				X				X				X				X	10.4.5
Pharmacokinetics					X						X								X	10.4.6
Anti-drug antibodies			X		X						X								X	10.4.7
Adverse events	X	X	X	X	X	X	X	X	X	X	X	X	X	X	X	X	X	X	X	11, Appendix 1, Appendix 2

¹⁾ For subjects who do not require a wash-out and subjects who only require washout of topical AD treatment (as specified in the exclusion criteria in Section 8.3), visits 1 and 2 will be combined and screening will be reduced to 2 weeks. Hence, these subjects will only attend visit 2 (Week -2) which will include all assessments shown under Week -6. The screening period has a maximum duration of 6 weeks.

²⁾ If the date of a subject visit does not conform to the trial plan, subsequent visits should be planned to maintain the visit schedule relative to randomisation/baseline.

Trial ID: LP0162-1339	Date: 29-Aug-2018	Version: 4.0
		Page 24 of 129

- 3) The informed consent form must be signed prior to performing any protocol-related procedures, including but not limited to screening evaluations and washout of disallowed medications.
- 4) Re-randomisation at Week 16: the treatment during the continuation treatment period will depend on the regimen received in the initial treatment period and on the subject's clinical response at Week 16 (see Section 7.1). Subjects will continue their use of TCS.

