- 5) All subjects must use an emollient twice daily (or more, as needed) for at least 14 days before randomisation and must continue this treatment throughout the trial (including safety follow-up).
- 6) For the first 3 IMP dosing visits (visits 3 to 5) and after re-randomisation (visits 11 to 13), subjects will be monitored after IMP administration for immediate drug reactions for a minimum of 30 minutes with vital signs taken at 30 minutes or until stable, whichever is later (see Section 9.1.3.1).
- 7) eDiary includes: Eczema-related Sleep NRS, Worst Daily Pruritus NRS, Average Daily Pruritus NRS, Patient Days of Topical Treatment Use, PGI-B, and PGI-S; subjects will complete daily from Week -2 to 32, except for Patient Days of Topical Treatment Use which will be completed daily from Week 0 to 32.
- 8) IgE not assessed at screening.

Abbreviations: BSA, body surface area; C-SSRS, Columbia-Suicide Severity Rating Scale; DLQI, Dermatology Life Quality Index; EASI, Eczema Area and Severity Index; EASI75, at least 75% reduction in EASI score; ECG, electrocardiogram; eDiary, electronic diary; EQ-5D-5L, EuroQoL 5 Dimension Health Questionnaire 5 Level; HADS, Hospital Anxiety and Depression Scale; IGA, Investigator's Global Assessment; IgE, immunoglobulin E; IMP, investigational medicinal product; NA, not applicable; NIMP, non-investigational medicinal product; NRS, numeric rating scale; PGI-B, Patient Global Impression of Bother; PGI-S, Patient Global Impression of Severity; POEM, Patient Oriented Eczema Measure; SCORAD, Scoring Atopic Dermatitis; TCS, topical corticosteroid.

Trial ID: LP0162-1339	Date: 29-Aug-2018	Version: 4.0
		Page 25 of 129

Panel 3 Schedule of trial procedures: follow-up including early termination

	SFU ¹ (end of trial)	Nominal Week 16 visit ² (if applicable)	Early termination ³	Unscheduled visit ⁴ (if	Details
Visit	20	11x	(if applicable)	applicable)	(protocol section)
Week	46	16			
Visit window (days)	±3	±3			
Trial products					
Concomitant medication/procedures	X	X	X	X^4	9.4, 9.5
IMP administration, compliance					
TCS (NIMP) dispensing				X ⁴	9.1.2, 9.1.3.2
TCS (NIMP) return			X	X ⁴	9.8.3.2, 9.8.5
Investigators global assessment of	efficacy				
IGA, EASI		X	X	X ⁴	10.3.1.1, 10.3.1.2
SCORAD		X	X	X ⁴	10.3.1.3
Atopic dermatitis flares			X	X ⁴	10.3.1.4
Subjects assessment of efficacy					
eDiary ⁵ completion		X	X	X ⁴	10.3.2
POEM		X	X	X ⁴	10.3.2.7
DLQI		X	X	X ⁴	10.3.2.8
EQ-5D-5L, HADS			X	X ⁴	10.3.2.9, 10.3.2.10
Safety assessments					

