5.1 Atopic dermatitis

Atopic dermatitis (AD) is a chronic inflammatory skin disease that may affect up to 20% of children and up to 10% of adults. In its severe form, AD is characterised by widespread skin lesions, intractable itch, as well as enhanced susceptibility to bacterial, viral, and fungal skin infections (1-4). AD is associated with a substantial patient burden that typically includes poor quality of life, sleep disturbance, and reductions in work productivity (5).

AD is characterised by an activated T-helper-2 (Th2) pathway with increased skin expression of key Th2 cytokines including interleukin (IL)-13 (6, 7). The expression of IL-13 is increased in lesional skin compared to non-lesional skin, and the proportion of CD4⁺ and CD8⁺ cells expressing IL-13 is upregulated in AD patients compared to individuals without AD (6, 8).

IL-13 acts on keratinocytes to release C-C motif chemokine 22 (CCL22) and recruit more IL-13 expressing Th2 cells, decrease differentiation, and contribute to decreased barrier function (9). IL-13 also drives immunoglobulin E (IgE) production and contributes to mast cell activation status and, once allergen cross-links IgE on the cell surface, drives histamine release and induces itch (10, 11). Indeed, itch is a key issue in AD, which drives significant mechanical damage to the skin and further facilitates allergen and pathogen entry.

These effects together drive and exacerbate the disease phenotype. A review of the available preclinical literature from mouse and human *ex vivo* models suggests IL-13 as a, if not the, central mediator of the AD skin phenotype. Indeed, there is evidence that blocking the IL-4 receptor (which is part of the receptor complex which also binds IL-13) with the monoclonal antibody dupilumab leads to clinical improvement in subjects with AD (12).

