9.2.1 Blinding

This is a double-blinded trial in which tralokinumab and placebo are visually distinct from each other. Neither the subject nor any of the investigator or LEO staff who are involved in the treatment or clinical evaluation and monitoring of the subjects will be aware of the treatment received.

The packaging and labelling of the IMPs will contain no evidence of their identity. IMP is packed in identical boxes, with non-sequential kit numbers to ensure that unblinding does not occur during shipment and handling of the drug.

Since tralokinumab and placebo are visually distinct and not matched for viscosity, IMP will be handled and administered by a qualified, unblinded HCP (trained site staff) at the site who will not be involved in the management of trial subjects and who will not perform any of the assessments.

If treatment allocation for a subject becomes known to the investigator or other trial staff involved in the management of trial subjects, LEO must be notified immediately.

Should an issue arise with the IMP (e.g., damaged kit or syringe that has been assigned to a subject prior to administration, or any other unexpected event with the kit or syringe [e.g., a malfunction during IMP administration]), the unblinded HCP at the site will contact the clinical research associate (CRA) to determine whether any specific actions are required.

Trial ID: LP0162-1339	Date: 29-Aug-2018	Version: 4.0
		Page 52 of 129

The trial site will maintain a written plan detailing which staff members are blinded/unblinded and the process of IMP administration used to maintain the blind.

To support submission for marketing approval, an analysis of trial data up to and including visit 19 (Week 32) will be performed and will require unblinding of data. To perform this analysis, an Analysis Group consisting of a Medical Expert, a Statistician, a Statistical Programmer and a Medical Writer will be unblinded to individual subject treatment allocation following database lock for the 32-week data. All staff involved in the conduct of the trial will remain blinded to treatment allocation for the entire duration of the trial. This principle will be applied to all investigator staff and to staff employed by the sponsor except for those who are directly involved in the execution of the analysis. See Section 12.3.11 for details regarding the statistical aspects of the analysis of data up to Week 32.

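### On-treatment IgE goes back to sites unmasked, and nothing keeps IGA/EASI raters from seeing it, so it may give a partial clue to the arm before Week 16

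*Protocol*

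**What the plan says.** **Sampling.** The row "Serum chemistry, haematology, IgE" in Panel 2 (Section 4) is marked at Week 0 and every 4 weeks to Week 32. A footnote adds "IgE not assessed at screening". Panel 3 repeats the row at the Week 46 safety follow-up and at early termination.

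**Reporting.** Panel 9 (Section 10.4.5) lists "Immunoglobulin E" under serology, and its only footnote concerns screening. The same section says "The central laboratory will provide results in SI units to trial sites in Europe and in conventional units to sites in North America", with no parameter held back. It also says "The investigator must evaluate all results outside the reference range", after which the report is signed, dated and filed.

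**Mechanism.** Section 5.1 states "IL-13 also drives immunoglobulin E (IgE) production and contributes to mast cell activation status". Section 5.2 describes tralokinumab as an antibody that binds IL-13 and blocks its receptor interaction.

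**Blinding.** Section 9.2.1 promises: "Neither the subject nor any of the investigator or LEO staff who are involved in the treatment or clinical evaluation" will know the treatment received. Its measures cover packaging, kit numbers, and the visible and viscosity differences between syringes, which are handled by an unblinded professional.

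**Raters.** Section 10.1 has trained investigators do the assessments, preferably the same one throughout for a given subject, and bars them from administering IMP. Section 7.4 says that observer bias is minimised.

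**The concern.** The protocol guards the blind on the injection side but not on the laboratory side. By its own account, IgE lies downstream of the drug target. An investigator with a baseline value and three on-treatment values could form a view of the arm from their course.

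Both primary endpoints are investigator ratings cut at a threshold (IGA 1 versus 2, and a 75% EASI reduction), so small shifts in borderline subjects change responder status. There is a second route. Rescue treatment is at the investigator's discretion (Section 9.6), and rescue before Week 16 makes the subject a non-responder (Section 12.3.5.1). The sensitivity analyses in Section 12.3.5 deal with missing data, discontinuation and rescue. None is aimed at a rater who has guessed the arm.

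**Working it through.** **1. Can an on-treatment IgE value reach a rater before the Week 16 rating?**
- Samples before Week 16 on the regular schedule: Week 0 (baseline), then Weeks 4, 8 and 12.
- Section 10.1 puts IGA and EASI before laboratory sampling within a visit, and IgE goes to a central laboratory. The Week 16 sample therefore cannot influence the Week 16 rating.
- That leaves three on-treatment values. A subject who stops IMP early may add one, because the early termination visit includes IgE and the nominal Week 16 visit, which includes IGA and EASI, follows it.
- Results go to the site, out-of-range values must be reviewed by the investigator, and raters are investigators. No text separates the two tasks. Appendix 4 lists raised serum IgE as a minor diagnostic feature of AD, so out-of-range values can be expected, but the share of subjects is not given.

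**2. Does a safety or eligibility rule need the value?** The laboratory criteria for permanent discontinuation in Section 9.7.1 name only ALT, AST and bilirubin. IgE is not measured at screening. The one remaining use is the general rule in Section 10.4.5 that clinically significant abnormal findings are reported as AEs.

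**3. The plan's own figure.** Section 12.1 gives n = 123 placebo and 246 active, 15% versus 30%, two-sided 5%, and 90% power. Using the pooled-variance z test:
- pooled rate = (123 × 0.15 + 246 × 0.30)/369 = 0.25
- SE under the null = √[0.25 × 0.75 × (1/123 + 1/246)] = 0.0478
- SE under the alternative = √[0.15 × 0.85/123 + 0.30 × 0.70/246] = 0.0435
- power = Φ[(0.15 − 1.96 × 0.0478)/0.0435] = 90.2%, which agrees with the plan.

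**4. Illustration only: an assumed rating drift.** Take a true IGA 0/1 rate of 15% in both arms and let ratings in the active arm drift upward by d. Then P(reject) = 1 − Φ[(1.96·SE0 − d)/SE1] + Φ[(−1.96·SE0 − d)/SE1], where SE0 is the pooled and SE1 the unpooled standard error. For d = 0.02, the pooled rate is 0.1633, SE0 = 0.0408 and SE1 = 0.0401, which gives 0.0674 + 0.0063 = 0.0737.

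| Assumed drift (points) | 0 | 1 | 2 | 3 | 5 |
|---|---|---|---|---|---|
| Two-sided type 1 error | 5.0% | 5.5% | 7.4% | 10.5% | 20.6% |

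**5. Illustration only: how well IgE might classify the arm.** If the IgE change differs between arms by s standard deviations, a reader using an equal-error cut is right with probability Φ(s/2). For s = 0.25, 0.5, 1.0, 1.5 and 2.0 this is 55%, 60%, 69%, 77% and 84%, against 50% by chance. The protocol gives no value for s, and nothing links steps 4 and 5.

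**The case against.** - **The premise is mechanism, not data.** Nothing in the protocol says that serum IgE falls on tralokinumab, how far, or whether it does so by Week 12. This stands, and it limits the point to a possible partial clue.
- **Signatory and rater may differ.** Section 10.4.5 names the investigator and Section 10.1 names trained investigators. No text says they are the same person. This stands too, but nothing keeps them apart.
- **The duty is narrow.** It asks whether an out-of-range value is clinically significant and does not ask for serial comparison. A value that returns to range triggers no review. That is true, but the results still reach the site and nothing prevents comparison.
- **Other evidence exists.** Worst Daily Pruritus NRS and DLQI are subject-reported and sit in the confirmatory hierarchy, so not all evidence depends on the rater. They are tested only after both primary endpoints succeed, and they do not correct a biased primary rating.
- **A laboratory manual, not shown, might mask IgE.** Its described content is collection, processing, storage, shipment, handling, destruction and contact details. The protocol's review rule covers all out-of-range results without exception.

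A reader might infer that IgE reveals the arm to the raters and that the type 1 error is inflated to a stated level. The documents do not support that. The drift figures would be the same for any source of rater bias and say nothing about IgE itself.

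**Conclusion.** The gap is real but of unknown size. Followed as written, the protocol returns a marker downstream of the drug target to sites unmasked, requires an investigator to review out-of-range values, and does not separate the IGA/EASI raters from them. The Week 4, 8 and 12 values may give a partial clue to the arm before the primary ratings. This rests on three things: the IL-13 to IgE link stated in Section 5.1, the absence of any masking text, and the possibility, not stated, that the laboratory reviewer also rates. The type 1 error figures (7.4% for a 2-point drift, 20.6% for 5 points) only show how sensitive the test is to an assumed drift. The sample size of 369 and the 90% power are unaffected. The change is worth making because it is specific and cheap, and no discontinuation or eligibility rule depends on IgE.

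**What to change.** State in Sections 9.2.1 and 10.4.5 that post-baseline IgE results, including early termination and Week 46:
- are withheld from blinded site and sponsor staff until the blind is broken at the end of the trial;
- go only to the clinical database, with access restricted accordingly, or to the unblinded group;
- are exempt from the out-of-range review in Section 10.4.5;
- are released on medical request to someone who does not rate that subject.

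Release at the Week 32 database lock would be too early. Section 9.2.1 keeps staff involved in trial conduct blinded for the whole trial, and Panel 3 takes a further IgE sample at Week 46.

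The cost is a short protocol addition and a change to the central laboratory reporting set-up. The investigator would no longer see on-treatment IgE routinely, so the exemption must also be reconciled with the AE reporting rule in Section 10.4.5. Sample size, power and significance level do not change.
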